11.2.2 Randomization and Enrollment of Subjects

Once an informed consent is obtained and study eligibility is confirmed, a study site member will obtain a subject number and the pharmacist or pharmacist designee will obtain a study drug assignment for each subject from a computer-generated randomization coding scheme using an Interactive Web-Based/Voice Response system (IXRS).

Subjects will be enrolled and randomized to the eravacycline or the ertapenem treatment arm in a 1:1 ratio.

For this study, enrollment is considered to occur at the time a subject is randomized (i.e., when the Investigator receives notification that the subject has been successfully randomized).

Randomization will be stratified based on two criteria: (1) by primary site of infection (pyelonephritis with normal urinary tract anatomy vs all other diagnoses) and (2) by the receipt of a single dose of effective non-study antibiotics for the acute cUTI within 72 hours prior to randomization. If a subject has abnormal anatomy *AND* pyelonephritis, then they will be classified as "abnormal anatomy" for stratification/analysis purposes and will be randomized to the "all other diagnoses" stratum. An enrollment cap of approximately 50% is planned for subjects with pyelonephritis with normal urinary tract anatomy. Also, an enrollment cap of approximately 20% is planned for subjects who have received a single dose of effective non-study antibiotics for the acute cUTI within 72 h prior to randomization.

The study will include approximately 130 sites globally. No site should enroll more than 50 subjects. Also, each site should ensure that no more than approximately 50% of their study subjects have a diagnosis of pyelonephritis with normal urinary tract anatomy. A site specific change to these randomization guidelines may be granted by the Sponsor as needed.

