15.2.1 Efficacy Analyses

The co-primary efficacy outcome measures are responder outcome in the micro-ITT population at the EOI and TOC visits (defined as 14-17 days after randomization). The responder rate will be determined as the number of subjects with clinical cure (i.e., complete or significant improvement of signs or symptoms such that no rescue/non-study antibacterial treatment is required) and microbiological success at the respective visit divided by the number of subjects in the analysis population (i.e., overall or by randomization strata). The number and percentage of subjects in each treatment group classified as a responder, non-responder and indeterminate at the EOI and TOC visits will be tabulated by treatment group in the micro-ITT population. Two-sided 95% CIs for the observed difference in responder rates (eravacycline treatment group minus ertapenem treatment group) at the EOI and TOC visits will be calculated using the method without stratification of Miettinen and Nurminen. If the lower limit of both 95% CIs for the difference in responder outcomes in the micro-ITT population exceeds -10%, then non-inferiority of eravacycline to ertapenem will be declared. The primary efficacy outcome will also be assessed across the randomization stratification factors of: (1) primary site of infection (pyelonephritis and normal urinary tract anatomy vs all other diagnoses) and (2) receipt of a single dose of effective non-study antibiotics for the acute cUTI within 72 hours prior to randomization. For each site of infection and prior antibiotic stratum, a 2-sided 95% CI for the observed difference in responder rates at the EOI and TOC visits will be calculated for the micro-ITT population.

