1.2. Study Design

1.2.1. Synopsis of Study Design

This is a non-inferiority (NI), phase 3, randomized, double-blind, double-dummy, multicenter, prospective study to assess the efficacy, safety, and PK of eravacycline compared with ertapenem. Dosing in the study arms is described in [Table 1](#).

Table 1 Study Drug Administration

Treatment Arms	For at Least the First 5 Doses	After EOI through Study Drug Completion
	IV Infusion	Oral Administration
Eravacycline (IV) / Levofloxacin (PO)	Eravacycline 1.5 mg/kg IV q24h	Levofloxacin 750mg PO QD
Ertapenem (IV) / Levofloxacin (PO)	Ertapenem 1.0 g IV q24h	Levofloxacin 750mg PO QD

Key: EOI = End of IV Therapy; IV= Intravenous; q24h= every 24 hours; QD=once daily. Randomization Methodology

Once an informed consent is obtained and study eligibility is established, a blinded study site member will obtain a subject number and a blinded study drug assignment for each subject from a computer-generated randomization scheme using an interactive web-based response system (IWRS). Randomization to eravacycline (1.5 mg/kg q24h) or ertapenem (1.0 g q24h) treatment arms will occur in a 1:1 ratio. For this study, enrollment is considered to occur at the time a subject is randomized. A subject is considered randomized when the IWRS issues a “confirmation of successful randomization” notification.

Randomization will be stratified based on 2 criteria: (1) by primary site of infection (pyelonephritis and normal urinary tract anatomy vs all other diagnoses) and (2) by the receipt of a single dose of effective non-study antibiotics for the acute cUTI within 72 hours of enrollment (yes vs no). An enrollment cap of approximately 50% is planned for subjects with pyelonephritis with normal urinary tract anatomy. Also, an enrollment cap of approximately 20% is planned for subjects who have received a single dose of effective non-study antibiotics for the acute cUTI within 72 hours of enrollment.

Approximately 1200 subjects will be randomized to receive study drug.

Subjects will be recruited at approximately 130 investigative sites worldwide.

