4. GENERAL STATISTICAL METHODS

4.1. Sample Size Justification

This study is designed to demonstrate NI of eravacycline to ertapenem in the co-primary efficacy measures of responder outcome at the EOI and TOC visits in the micro-ITT population. An NI margin of 10% will be used which is based on historical data regarding the treatment effect of antibiotics. A 10% NI margin for the efficacy measure of responder outcome is robust and can sufficiently confirm a clinically meaningful treatment effect of eravacycline in the treatment of cUTI.

The sample size calculation is based on ensuring sufficient power for the co-primary efficacy outcomes for the FDA as well as the co-primary efficacy outcomes for the EMA (which are secondary efficacy outcomes for the FDA). Using a 10% NI margin, one-sided alpha of 0.025, 80% power, response rates at TOC of 71% in the eravacycline group and 72% in the ertapenem group, and the sample size methodology of Farrington and Manning, a total of 395 subjects per arm in the micro-ITT population is required. This sample size provides >90% power for the response rates at EOI assuming the response rates are 93% and 94% in the eravacycline and ertapenem groups, respectively. A sample size of approximately 1200 randomized subjects should provide sufficient numbers for this study, assuming 66% of enrolled subjects will meet the requirements for inclusion in the micro-ITT population.

For the EMA, it is assumed that 65% of the randomized subjects will be in the micro-MITT population and 60% in ME population. The microbiological success rates at TOC are assumed to be 79% and 82% in both treatment groups in the micro-MITT and ME populations, respectively. With these assumptions, using an NI margin of 10%, a one-sided alpha of 0.005, and the sample size methodology of Farrington and Manning, there is at least 80% power to show NI for the co-primary efficacy outcomes. The power calculations are summarized in [Table 3](#) based on a total of 1200 randomized subjects.

Table 3 Assumptions of Sample Size Calculations

Outcome/Population	Alpha level (one-sided)	Evaluability Rate	Outcome Rates		Total N	Power
			ERV	ERT		
FDA Outcomes						
Responder at EOI/micro-ITT	0.025	66%	93%	94%	790	>99%
Responder at TOC/micro-ITT	0.025	66%	71%	72%	790	80.0%
EMA Outcomes						
Microbiological Success at	0.005	65%	79%	79%	780	79.8%

TOC / micro-MITT						
Microbiological Success at TOC / ME-TOC	0.005	60%	82%	82%	720	84.7%

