5.7. Efficacy Evaluation

For all efficacy analyses, subjects will be analyzed in the group to which they were randomized. By definition, subjects who receive the wrong study drug are not included in the CE and ME populations. For the primary analysis, subjects who are randomized to the wrong primary site of infection stratum will be analyzed in the stratum to which they were randomized.

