Failure	Indeterminate / Missing	Non-responder
Indeterminate / Missing	Success	Indeterminate
Indeterminate / Missing	Failure	Non-responder
Indeterminate / Missing	Indeterminate / Missing	Indeterminate

For the micro-ITT population, the proportion of micro-ITT subjects with a response is defined using the following formula (where the denominator adds to the total number of subjects in the micro-ITT population):

Number of subjects with response

(Number of subjects with a response + Number of subjects with a non-response + Number of subjects with an indeterminate response)

The primary efficacy analyses will be based on the micro-ITT population. The NI test will be a one-sided hypothesis test performed at the 2.5% level of significance. This NI test will be based on the lower limit of the two-sided 95% confidence interval (CI) for both EOI and TOC Visits. The primary efficacy outcome is the percentage of subjects with an outcome of responder (clinical cure and microbiological success) at the EOI and TOC Visits. The primary analysis is unadjusted.

The number and percentage of subjects in each treatment group defined as a responder, non-responder and indeterminate/missing will be tabulated. The null and alternative hypotheses are as follows:

$$H_0: p_1 - p_2 \leq -\Delta \text{ and } H_1: p_1 - p_2 > -\Delta$$

Where p_1 is the responder rate in the eravacycline treatment group, p_2 is the responder rate in the ertapenem treatment group, and Δ is the NI margin of 10%. Note: For H_0 , outcomes at both EOI and TOC visits will be considered. For H_1 , outcomes at EOI or TOC visits will be considered.

To test the null hypothesis, two-sided 95% CIs for the observed difference in responder rates (eravacycline treatment group minus ertapenem treatment group) will be calculated for the micro-ITT population for the EOI and TOC Visits. If the lower limit of both (EOI and TOC Visits) 95% CIs for the difference in responder rates in the micro-ITT analysis set exceeds – 10%, then the null hypothesis will be rejected and the NI of eravacycline to ertapenem will be declared.

The two-sided 95% CIs for NI testing based on the difference of responder rates at the EOI and TOC Visits, will be computed using the method proposed without stratification by Miettinen and Nurminen (Miettinen 1985). For notation purposes, assume 1 represents the eravacycline group (Group 1) and 2 represents the ertapenem group (Group 2).

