5.7.1.1. Additional Analyses of the Primary Efficacy Outcome

If eravacycline is determined to be non-inferior to ertapenem, superiority of eravacycline to ertapenem will be assessed. A step-wise analysis will be conducted in which superiority at TOC will be tested first. If the lower bound of the 2-sided 95% CI is greater than 0, superiority of eravacycline for response (clinical cure and microbiological success) at the TOC visit will be concluded and superiority at EOI will be tested. If the lower bound of the 2-sided 95% CI is greater than 0, superiority of eravacycline for response (clinical cure and microbiological success) at the EOI visit will be concluded. If superiority is not concluded at the TOC visit, superiority at the EOI visit will not be tested.

The reasons for non-response and for an indeterminate response at the EOI and TOC visits will be summarized by treatment group for the micro-ITT population. The primary efficacy outcome will also be assessed separately across the randomization stratification factors of primary site of infection and receipt of a single dose of effective non-study antibiotics. For each infection site stratum and each antibiotic stratum, a 2-sided 95% CI for the observed difference in the responder rate at the EOI and TOC visits will be calculated for the micro-ITT population using the same method as for the primary efficacy analysis. In addition, the primary analysis results will also be assessed separately across geographical region and country by treatment group to assess for consistency of results across regions. For each geographical region and country, a 2-sided 95% CI for the observed difference in the response rate at the EOI and TOC visits will be calculated for the micro-ITT population.

Sensitivity analyses of the primary outcome will also be conducted. The first analysis will be an adjusted analysis (adjusted for the stratification factor of primary site of infection and receipt of a single dose of effective non-study antibiotics). A 2-sided stratified 95% CI will be computed for the difference in responder rate at the EOI and TOC visits between the eravacycline and ertapenem treatment groups using the method of Miettinen and Nurminen (9). Cochran-Mantel-Haenszel weights will be used for the stratum weights in the calculation of the CI as follows:

$$W_i = \frac{n_{1i}n_{2i}}{n_{1i} + n_{2i}}$$

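### Randomisation is stratified on two factors but the FDA primary confidence intervals are not; promoting the stratified interval already in the SAP costs nothing material and gains a little power at TOC if the strata predict response.

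*SAP*

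**What the plan says.** - SAP 1.2.1: "Randomization will be stratified based on 2 criteria". The factors are primary site of infection (pyelonephritis with normal anatomy against all other diagnoses) and receipt of one effective non-study antibiotic dose in the preceding 72 hours.
- Both factors carry enrolment caps. About 50% applies to the pyelonephritis stratum. For the other factor, protocol 11.2.2 says "an enrollment cap of approximately 20% is planned for subjects who have received a single dose of effective non-study antibiotics".
- SAP 5.7.1, on the EOI and TOC comparison in the micro-ITT population: "The primary analysis is unadjusted". Protocol 15.2.1 agrees: the intervals are "calculated using the method without stratification of Miettinen and Nurminen".
- SAP 5.7.1.1, on sensitivity analyses: "The first analysis will be an adjusted analysis", on both stratification factors, and "Cochran-Mantel-Haenszel weights will be used for the stratum weights in the calculation of the CI".
- SAP 5.7 attaches an as-randomised rule to the primary analysis, which reads as follows: "subjects who are randomized to the wrong primary site of infection stratum will be analyzed in the stratum to which they were randomized".
- SAP 4.1: "a total of 395 subjects per arm in the micro-ITT population is required". This is an unstratified Farrington-Manning calculation.
- Protocol 15.2.1 uses the stratified form of the same method for the EMA co-primary analyses. Neither document gives a reason for the difference.

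**The concern.** When randomisation is balanced within strata and the strata predict response, the observed difference between arms varies less than an unstratified variance formula assumes. The unstratified interval is then slightly too wide, so the test is mildly conservative and gives up some power. This matters only at TOC, which sets the sample size and has no reserve above 80%. EOI is already above 99%, and both visits must succeed, so any gain at TOC passes almost entirely to the trial's overall chance of success.

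There is a smaller drafting problem. The as-randomised stratum rule in SAP 5.7 is attached to the primary analysis, where no strata are used. It can serve the by-stratum summaries and the stratified interval in 5.7.1.1. However, it covers only the site factor, so nothing says how subjects placed in the wrong prior-antibiotic stratum are handled.

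**Working it through.** **Inputs from the documents.** TOC rates 71% and 72%, EOI rates 93% and 94%, margin 10 points, one-sided alpha 0.025, 395 micro-ITT subjects per arm, 1200 randomised 1:1 (SAP 4.1). Stratum shares of 50% and 20% are taken from the caps.

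**Assumed.** Response gaps between strata, written as site gap / prior-antibiotic gap in percentage points. The documents give none.

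**1. Reproduce the plan's figure.** The power is

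Φ{[(p1 − p2 + 0.10) − 1.96 √(S0/n)] / √(S1/n)},

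where S1 = 0.71×0.29 + 0.72×0.28 = 0.4075, and S0 is the same sum at the constrained estimates (0.6603 and 0.7603), giving 0.4065. With n = 395 the standard errors are 0.03208 (null) and 0.03212 (alternative). Power = Φ[(0.09 − 0.0629)/0.0321] = 80.1%, against 80.0% stated. The same formula at EOI gives 99.8%, against >99% stated.

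**2. Variance that stratification removes.** With independent factors, the between-stratum variance per arm is B = 0.5×0.5×(site gap)² + 0.2×0.8×(antibiotic gap)², and the proportion removed is 2B/S1.

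- 10/10: B = 0.0025 + 0.0016 = 0.0041, and 0.0082/0.4075 = 2.0%.
- 20/0: B = 0.0100, and 0.0200/0.4075 = 4.9%.
- 20/10: B = 0.0116, and 0.0232/0.4075 = 5.7%.

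For 20/0, both tests have actual standard error √(0.3875/395) = 0.0313. The unstratified test still uses 0.0321 for its null standard error, which gives 80.7%. The stratified test uses √(0.3865/395) = 0.0313, which gives 82.0%.

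**3. Simulation.** 400,000 trials per scenario: 600 randomised per arm, balanced within four strata; micro-ITT membership binomial at 790/1200, so that the arms need not balance within strata. The unstratified score test at −10 points is compared with the CMH-weighted stratified one. Monte Carlo standard error is about 0.06 points for power and 0.025 for error.

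| Assumed gaps (site/antibiotic) | TOC power, unstratified | TOC power, stratified | One-sided error, unstratified | One-sided error, stratified |
|---|---|---|---|---|
| 0/0 | 80.1% | 80.0% | 2.5% | 2.5% |
| 10/10 | 80.2% | 80.7% | 2.4% | 2.5% |
| 15/0 | 80.3% | 81.1% | not listed | not listed |
| 20/0 | 80.5% | 81.9% | 2.35% | 2.5% |
| 20/10 | 80.5% | 82.1% | 2.3% | 2.5% |

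Independent re-runs with other seeds agree closely on power. At EOI, with a 5-point site gap, both tests have 99.8% power.

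**4. In subjects.** For equal precision, 4.9% of 790 is about 39 micro-ITT subjects (20/0), and 2.0% of 790 is about 16 (10/10; about 14 by simulation). These express the efficiency gain; no cut in sample size is proposed.

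**5. Small strata.** At the caps, the smallest cell has 0.5×0.2×395 ≈ 40 per arm. If only 5% have had a prior dose, it has 0.5×0.05×395 ≈ 10 per arm. The gains are then 0.4 points (10/10) and 1.4 points (20/0), with stratified error 2.5%. At a 2% share they are 0.3 and 1.4 points, again with error 2.5%.

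**The case against.** The strongest reply is that nothing is broken. The unstratified interval is valid, agrees between protocol and SAP, and matches the sample-size method, and the stratified interval will be reported anyway. All of that stands, and it is why this is only a suggestion.

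The gain is also small and rests on assumed gaps. With 5 points on each factor it is about 0.1 point. If the site split is 30/70, the 20/0 gain falls from about 1.4 to about 1.1 points; if 10% of subjects are placed in the wrong site stratum (an assumption), it falls to about 0.9. These limits are real, but they shrink the benefit without creating a cost.

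The blinded reassessment at about 800 subjects (protocol 9.1 and 15.4, SAP 4.7) already protects power. It does so by adding subjects, and does not recover the efficiency lost by ignoring the strata.

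The unstratified FDA and stratified EMA analyses in protocol 15.2.1 may be a deliberate split. No reason is given, and the EMA choice shows that the sponsor accepts stratified inference for a confirmatory claim. If there is an FDA-specific reason, the SAP should state it.

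Finally, a sparse-cell rule is hardly needed on these results, since error holds at 2.5% without it. That is fair; the rule is optional.

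**Conclusion.** The point holds as an optional improvement. The planned primary analysis is valid and at worst slightly conservative. Stratifying it adds about 0.5 point of TOC power if response differs by 10 points on both factors, and about 1.4 to 1.6 points with a 20-point site gap. With no gap the difference is 0.1 point or less. Stratified one-sided error is about 2.5% in every scenario where it was computed. The size depends on assumed stratum gaps, on site shares near 50/50 and on correct stratum assignment; the absence of a material downside does not depend on a gap being present. Separately, the SAP 5.7 stratum rule needs rewording whichever interval is primary.

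**What to change.** Before unblinding:

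1. SAP 5.7.1 and protocol 15.2.1: make the stratified Miettinen-Nurminen 95% interval with CMH weights primary at EOI and TOC, using both factors as randomised, and report the CMH-weighted difference with it. Replace the unstratified variance formula in 5.7.1 with the stratified one.
2. SAP 5.7.1.1: use the same interval for the superiority steps, and make the unstratified interval the first sensitivity analysis.
3. SAP 5.7: extend the as-randomised rule to the prior-antibiotic stratum.
4. Optionally, fix a sparse-cell rule on blinded counts. For example: if any of the four cells has fewer than 20 micro-ITT subjects across both arms, stratify by site only. At a 5% prior-antibiotic share this would apply in about 70% of simulated trials, with power within 0.1 point of the four-cell analysis and one-sided error of 2.5%.

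If the unstratified interval stays primary, reword SAP 5.7 so that the rule refers to the by-stratum and stratified analyses and covers both factors.

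The cost is wording in SAP 5.7, 5.7.1 and 5.7.1.1 and in protocol 15.2.1. The margin, the sample size and the data collected do not change.

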5.7.1.1. Additional Analyses of the Primary Efficacy Outcome

If eravacycline is determined to be non-inferior to ertapenem, superiority of eravacycline to ertapenem will be assessed. A step-wise analysis will be conducted in which superiority at TOC will be tested first. If the lower bound of the 2-sided 95% CI is greater than 0, superiority of eravacycline for response (clinical cure and microbiological success) at the TOC visit will be concluded and superiority at EOI will be tested. If the lower bound of the 2-sided 95% CI is greater than 0, superiority of eravacycline for response (clinical cure and microbiological success) at the EOI visit will be concluded. If superiority is not concluded at the TOC visit, superiority at the EOI visit will not be tested.

The reasons for non-response and for an indeterminate response at the EOI and TOC visits will be summarized by treatment group for the micro-ITT population. The primary efficacy outcome will also be assessed separately across the randomization stratification factors of primary site of infection and receipt of a single dose of effective non-study antibiotics. For each infection site stratum and each antibiotic stratum, a 2-sided 95% CI for the observed difference in the responder rate at the EOI and TOC visits will be calculated for the micro-ITT population using the same method as for the primary efficacy analysis. In addition, the primary analysis results will also be assessed separately across geographical region and country by treatment group to assess for consistency of results across regions. For each geographical region and country, a 2-sided 95% CI for the observed difference in the response rate at the EOI and TOC visits will be calculated for the micro-ITT population.

Sensitivity analyses of the primary outcome will also be conducted. The first analysis will be an adjusted analysis (adjusted for the stratification factor of primary site of infection and receipt of a single dose of effective non-study antibiotics). A 2-sided stratified 95% CI will be computed for the difference in responder rate at the EOI and TOC visits between the eravacycline and ertapenem treatment groups using the method of Miettinen and Nurminen (9). Cochran-Mantel-Haenszel weights will be used for the stratum weights in the calculation of the CI as follows:

$$W_i = \frac{n_{1i}n_{2i}}{n_{1i} + n_{2i}}$$

Where n_{1i} is the number of subjects in the eravacycline treatment group (Group 1) in the i -th stratum, and n_{2i} is the number of subjects in the ertapenem treatment group (Group 2) in the i -th stratum.

The second sensitivity analysis will analyze those subjects who are considered indeterminates in the primary analysis as responders. Additional sensitivity analyses will be stratified analyses for the following combinations: primary site of infection and geographic region, primary site of infection and receipt of a single dose of effective non-study antibiotics, and geographic region and receipt of a single dose of effective non-study antibiotics. Two-sided 95% CIs will be computed for the difference in responder rate at the EOI and TOC visits between the eravacycline and ertapenem treatment groups within each stratum using the method of Miettinen and Nurminen.

